9.0 LABELING, PACKAGING, STORAGE AND RETURN OF CLINICAL SUPPLIES

9.1 Investigational Product

The investigator shall take responsibility for and shall take all steps to maintain appropriate records and ensure appropriate supply, storage, handling, distribution and usage of investigational product in accordance with the protocol and any applicable laws and regulations.

Clinical Supplies will be provided by Merck as summarized in Table 7.

Table 7 Product Descriptions

Product Name & Potency	Dosage Form
Pembrolizumab 50 mg	Lyophilized Powder for Injection
Pembrolizumab 100 mg/ 4mL	Solution for Injection

9.2 Packaging and Labeling Information

Clinical supplies will be affixed with a clinical label in accordance with regulatory requirements.

9.3 Clinical Supplies Disclosure

This trial is open-label; therefore, the subject, the trial site personnel, the Sponsor and/or designee are not blinded to treatment. Drug identity (name, strength) is included in the label text; random code/disclosure envelopes or lists are not provided.

9.4 Storage and Handling Requirements

Clinical supplies must be stored in a secure, limited-access location under the storage conditions specified on the label.

Receipt and dispensing of trial medication must be recorded by an authorized person at the trial site.

Clinical supplies may not be used for any purpose other than that stated in the protocol.

9.5 Returns and Reconciliation

The investigator is responsible for keeping accurate records of the clinical supplies received from Merck or designee, the amount dispensed to and returned by the subjects and the amount remaining at the conclusion of the trial.

Upon completion or termination of the study, all unused and/or partially used investigational product will be destroyed at the site per institutional policy. It is the Investigator's responsibility to

arrange for disposal of all empty containers, provided that procedures for proper disposal have been established according to applicable federal, state, local and institutional guidelines and procedures, and provided that appropriate records of disposal are kept.

10.2 Compliance with Financial Disclosure Requirements

Financial Disclosure requirements are outlined in the US Food and Drug Administration Regulations, Financial Disclosure by Clinical Investigators (21 CFR Part 54). It is the Sponsor's responsibility to determine, based on these regulations, whether a request for Financial Disclosure information is required. It is the investigator's/subinvestigator's responsibility to comply with any such request.

The investigator/subinvestigator(s) agree, if requested by the Sponsor in accordance with 21 CFR Part 54, to provide his/her financial interests in and/or arrangements with the Sponsor to allow for the submission of complete and accurate certification and disclosure statements.

The investigator/subinvestigator(s) further agree to provide this information on a Certification/Disclosure Form, commonly known as a financial disclosure form, provided by the Sponsor or through a secure password-protected electronic portal provided by the Sponsor. The investigator/subinvestigator(s) also consent to the transmission of this information to the Sponsor in the United States for these purposes. This may involve the

transmission of information to countries that do not have laws protecting personal data.

10.3 Compliance with Law, Audit and Debarment

By signing this protocol, the investigator agrees to conduct the trial in an efficient and diligent manner and in conformance with this protocol; generally accepted standards of Good Clinical Practice (e.g., International Conference on Harmonization of Technical Requirements for Registration of Pharmaceuticals for Human Use Good Clinical Practice: Consolidated Guideline and other generally accepted standards of good clinical practice); and all applicable federal, state and local laws, rules and regulations relating to the conduct of the clinical trial. The Code of Conduct, a collection of goals and considerations that govern the ethical and scientific conduct of clinical investigations sponsored by Merck, is provided in Section 12.1 - Merck Code of Conduct for Clinical Trials. The investigator also agrees to allow monitoring, audits, IRB/ERC review and regulatory authority inspection of trial-related documents and procedures and provide for direct access to all trial-related source data and documents. The investigator agrees not to seek reimbursement from subjects, their insurance providers or from government programs for procedures included as part of the trial reimbursed to the investigator by the Sponsor.

The investigator shall prepare and maintain complete and accurate trial documentation in compliance with Good Clinical Practice standards and applicable federal, state and local laws, rules and regulations; and, for each subject participating in the trial, provide all data, and, upon completion or termination of the clinical trial, submit any other reports to the Sponsor as required by this protocol or as otherwise required pursuant to any agreement with the Sponsor. Trial documentation will be promptly and fully disclosed to the Sponsor by the investigator upon request and also shall be made available at the trial site upon request for inspection, copying, review and audit at reasonable times by representatives of the Sponsor or any regulatory authorities. The investigator agrees to promptly take any reasonable steps that are requested by the Sponsor as a result of an audit to cure deficiencies in the trial documentation and worksheets/case report forms.

The investigator must maintain copies of all documentation and records relating to the conduct of the trial in compliance with all applicable legal and regulatory requirements. This documentation includes, but is not limited to, the protocol, worksheets/case report forms, advertising for subject participation, adverse event reports, subject source data,

correspondence with regulatory authorities and IRBs/ERCs, consent forms, investigator's curricula vitae, monitor visit logs, laboratory reference ranges, laboratory certification or quality control procedures and laboratory director curriculum vitae. By signing this protocol, the investigator agrees that documentation shall be retained until at least 2 years after the last approval of a marketing application in an ICH region or until there are no pending or contemplated marketing applications in an ICH region or until at least 2 years have elapsed since the formal discontinuation of clinical development of the investigational product. Because the clinical development and marketing application process is variable, it is anticipated that the retention period can be up to 15 years or longer after protocol database lock. The Sponsor will determine the minimum retention period and notify the investigator when documents may be destroyed. The Sponsor will determine the minimum retention period and upon request, will provide guidance to the investigator when documents no longer need to be retained. The sponsor also recognizes that documents may need to be retained for a longer period if required by local regulatory requirements. All trial documents shall be made available if required by relevant regulatory authorities. The investigator must consult with and obtain written approval by the Sponsor prior to destroying trial and/or subject files.

ICH Good Clinical Practice guidelines recommend that the investigator inform the subject's primary physician about the subject's participation in the trial if the subject has a primary physician and if the subject agrees to the primary physician being informed.

The investigator will promptly inform the Sponsor of any regulatory authority inspection conducted for this trial.

Persons debarred from conducting or working on clinical trials by any court or regulatory authority will not be allowed to conduct or work on this Sponsor's trials. The investigator will immediately disclose in writing to the Sponsor if any person who is involved in conducting the trial is debarred or if any proceeding for debarment is pending or, to the best of the investigator's knowledge, threatened. In the event the Sponsor prematurely terminates a particular trial site, the Sponsor will promptly notify that trial site's IRB/IEC.

For a single-center trial, the Protocol CI is the principal investigator. In addition, the Sponsor must designate a principal or coordinating investigator to review the trial report that summarizes the trial results and confirm that, to the best of his/her knowledge, the report accurately describes the conduct

and results of the trial [Clinical Study Report (CSR) CI]. The Sponsor may consider one or more factors in the selection of the individual to serve as the Protocol CI and or CSR CI (e.g., availability of the CI during the anticipated review process, thorough understanding of clinical trial methods, appropriate enrollment of subject cohort, timely achievement of trial milestones). The Protocol CI must be a participating trial investigator.

10.4 Compliance with Trial Registration and Results Posting Requirements

Under the terms of the Food and Drug Administration Modernization Act (FDAMA) and the Food and Drug Administration Amendments Act (FDAAA), the Sponsor of the trial is solely responsible for determining whether the trial and its results are subject to the requirements for submission to the Clinical Trials Data Bank, <http://www.clinicaltrials.gov>. Information posted will allow subjects to identify potentially appropriate trials for their disease conditions and pursue participation by calling a central contact number for further information on appropriate trial locations and trial site contact information.

10.5 Quality Management System

By signing this protocol, the Sponsor agrees to be responsible for implementing and maintaining a quality management system with written development procedures and functional area standard operating procedures (SOPs) to ensure that trials are conducted and data are generated, documented, and reported in compliance with the protocol, accepted standards of Good Clinical Practice, and all applicable federal, state, and local laws, rules and regulations relating to the conduct of the clinical trial.

10.6 Data Management

The investigator or qualified designee is responsible for recording and verifying the accuracy of subject data. By signing this protocol, the investigator acknowledges that his/her electronic signature is the legally binding equivalent of a written signature. By entering his/her electronic signature, the investigator confirms that all recorded data have been verified as accurate. The investigator will have access to all study related events and outcomes and will have license to analyze and publish this data as he deems fit without any limitations.

The OnCore Database will be utilized, as required by the Case Comprehensive Cancer Center, to provide data collection for both accrual entry and trial data management. OnCore is a Clinical Trials Management System housed on secure servers maintained at Case Western Reserve University. OnCore properly used is compliant with Title 21 CFR Part 11. Access to data through OnCore is restricted by user accounts and assigned roles. Once logged into the OnCore system with

a user ID and password, OnCore defines roles for each user which limits access to appropriate data. User information and password can be obtained by contacting the OnCore Administrator at [contact].

OnCore is designed with the capability for study setup, activation, tracking, reporting, data monitoring and review, and eligibility verification. This study will utilize electronic Case Report Form completion in the OnCore database. A calendar of events and required forms are available in OnCore.

This protocol will adhere to the policies of the Case Comprehensive Cancer Center Data and Safety Monitoring Plan in accordance with NCI regulations.

Registry Integration

CASE 4311 registry (IRB CC 00192), will share data with IRB 17-069. Data shared will only pertain to mutual patients consented to IRB 17-069 and patients eligible for inclusion in CASE 4311. The clinical data collected by CASE 4311/IRB CC 00192, particularly data regarding cancer recurrence, will be used in conjunction with data collected under IRB 17-069.

10.7 APPENDICES

10.8 ECOG Performance Status

Grade	Description
0	Normal activity. Fully active, able to carry on all pre-disease performance without restriction.
1	Symptoms, but ambulatory. Restricted in physically strenuous activity, but ambulatory and able to carry out work of a light or sedentary nature (e.g., light housework, office work).
2	In bed <50% of the time. Ambulatory and capable of all self-care, but unable to carry out any work activities. Up and about more than 50% of waking hours.
3	In bed >50% of the time. Capable of only limited self-care, confined to bed or chair more than 50% of waking hours.
4	100% bedridden. Completely disabled. Cannot carry on any self-care. Totally confined to bed or chair.
5	Dead.
*As published in Am. J. Clin. Oncol.: Oken, M.M., Creech, R.H., Tormey, D.C., Horton, J., Davis, T.E., McFadden, E.T., Carbone, P.P.: Toxicity And Response Criteria Of The Eastern Cooperative Oncology Group. Am J Clin Oncol 5:649-655, 1982. The Eastern Cooperative Oncology Group, Robert Comis M.D., Group Chair.	

10.9 Common Terminology Criteria for Adverse Events V4.0 (CTCAE)

The descriptions and grading scales found in the revised NCI Common Terminology Criteria for Adverse Events (CTCAE) version 4.0 will be utilized for adverse event reporting. (<http://ctep.cancer.gov/reporting/ctc.html>)

Appendix 10.10 – Tissue and Blood processing for correlative science

Study #1: Specimen Collection for PD-L1 Expression			

 All patients will have slides cut from FFPE tissue blocks for analysis of PD-L1 expression by IHC staining FFPE tissue will be obtained from the Tissue Procurement and/or pathology department (CCF) or Biorepository and/or pathology department (UH) and assigned a unique identification number. All other PHI will be redacted from the pathology report. Five slides will be cut from each FFPE block for PD-L1 and H&E staining. 
 One slide each for H&E, PD-L1, and Isotype and two for repeat staining if needed Results: QualTek Molecular Laboratories Clinical Laboratories will report to Merck and study investigators. Residual Material: FFPE specimens will be retained by Cleveland Clinic and University Hospitals in anatomic pathology per their routine, and made available for future use as indicated. 
Study #1 Specimens shipped to:
 
QualTekMolecularLaboratories MISP Receiving [name] [name] [contact] [contact] [contact]
			
Specimen Type	Collection Time Points	Collection Information and Requirements	Shipping
Five slides from primary tumor FFPE blocks	Baseline Tumor specimen	Sections will be 4 micron thickness onto Fisher ProbeOn Plus Slides, Cat Number 22-230-900. Tissue sections must be placed on the painted/textured side of the slide.	Slides shipped cold (2-8°C) and in the dark using QualTek-supplied packing materials.

Study #2: Blood Collection for Immune Biomarker Analysis

- All patients will have blood collected at specific time points (pre-treatment and weeks 7, 20, and 52). +/- 4 weeks is allowed on follow up visits.
- At each time point, up to 50cc of blood will be collected and processed by research laboratory personnel ([name], PI) to isolate lymphocytes and freeze for further analysis.
- Specimens will be assigned the same unique identification number used for Study #1 and any other personal health information (PHI) will be redacted from the pathology report.
- Results: Research laboratory personnel will report to Merck and study investigators.
- Residual Material: cryopreserved specimens will be retained by the research laboratory until the study conclusion.

For CC: Samples will typically be collected by CRA. [name] lab will then be contacted as follows:

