3.2 Secondary Objective(s) & Hypothesis(es)

(1) **Objective:**

- 5) To evaluate the relationship of baseline PD-L1 expression by tumor and tumor-infiltrating lymphocytes (TILs) to preliminary efficacy .
- 6) To phenotype tumor infiltrating lymphocytes and peripheral blood lymphocytes (PBLs), and investigate tumor suppressor populations including Tregs, MDSCs and CD8 suppressor

cells and assess ex vivo for effector function by cytokine production and cytotoxicity assays as well as suppressor function in assays with autologous PBLs.

- 7) For those participants for whom tumor tissue is available, we will evaluate the tumor microenvironment (TME), and immune markers at the invasive margin of the tumor, including CD8, PD-1, PD-L1, TIM-3, galectin-9 or HMGB-1, BTLA and HVEM, as well as Lag-3, CTLA-4 and others.
- 8) If sufficient tumor is available, we will also evaluate the genomic and/or transcriptomic profile of a subset of tumors using RNA-seq /Whole Transcriptome Shotgun Sequencing

Hypotheses:

- 1) Baseline PD-L1 expression will not be associated with 1yr PFS.
- 2) Peripheral immune profiles on PBMC will dynamically change from baseline through treatment and after completion of therapy and correlate with 1yr PFS.
- 3) Changes in the TME at the marginal edge of the tumor will correlate with 1yr PFS and be marker dependent.
- 4) Baseline genomic/proteomic tumor profiles will correlate with 1yr PFS

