4.2.3.3 Rationale for Correlative Endpoints/Biomarker Research

Central hypothesis: Cutaneous squamous cell carcinoma (CSCC) is responsive to combination of PD-1 inhibition and radiation therapy.

To test our hypothesis correlatively we propose the following aims:

Aim 1. To correlate baseline PD-1 expression in the tumor with disease related outcomes.

Rationale: It is unknown whether patients with tumors that express higher levels of PD-1 preferentially respond compared to those that do not. As such, this will be systematically evaluated on all patients.

Research Plan: FFPE tissue blocks will be collected from patients and slides will be cut for subsequent biomarker staining. Analysis of PD-L1 expression will be performed by immunohistochemical staining using the Merck assay. Either complete circumferential or partial linear plasma membrane staining will constitute positive PD-L1 staining. A cut-off of $\geq 5\%$ tumor cell membrane staining will be reported as positive.

Aim 2. To define response to radiation/PD-1 inhibition based on tumor microenvironment and peripheral blood alterations in patients with CSCC.

Rationale: Many solid tumors do respond to checkpoint inhibitors. Little is known in regards to CSCC patients who will or will not respond to the proposed treatment regimen of post-operative radiation and anti-PD-1 therapy.

Research Plan: Prospectively we will stratify study patients into two groups: those that do, or do not respond to the proposed therapy based on historical published data from our institution. The following are the proposed assays for evaluation.

A. Peripheral Blood Lymphocytes

Flow cytometry: Peripheral blood samples drawn from patients pretreatment and at specified times post treatment will be isolated by centrifugation. Surface biomarker expression will be assessed by FACS similar to the analysis of tumor-resident lymphocytes. Staining will evaluate CD3, CD4, CD8 expression as well as cytotoxic markers (perforin, FasL, Granzyme A&B, markers of dysfunction/exhaustion (PD-1, TIM-3, Lag-3), and markers characteristic of regulatory cells (Foxp3, CD25, GITR, CD27, CD28) and markers for myeloid derived suppressor cells. Finally, we will assess TCR clonal diversity using PCR methods.

B. Tissue

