6.0 TRIAL FLOW CHART

6.1 Study Flow Chart

		Study Treatment (weeks)										Post- tx	Long term f/u	
		1	2	3	4	5	6	7	10	13	16			20 ^f
Medical History, PE, Vital Signs	x	x	x	x	x	x	x	x	x	x	x	x	x	x
Height	x													
Weight	x	x	x	x	x	x	x	x	x	x	x	x	x	x
ECOG PS	x	x	x	x	x	x	x	x	x	x	x	x	x	x
CBC with Differential	x	x			x			x	x	x	x	x	x	x
Complete metabolic panel	x	x			x			x	x	x	x	x	x	x
Concomitant meds	x	x			x			x	x	x	x	x	x	x
Pregnancy test ^b	x													
TSH	x	x			x			x	x	x	x	x	x	x
Immune Status History	x													

CT neck and chest (with contrast if possible) ^c (CT Chest preferred, CXR acceptable)	x												x	x
PET/CT and/or MRI ^c (optional)	x													
Dental evaluation ^d	x													
Pembrolizumab		x			x			x	x	x	x			
IMRT			x	x	x	x	x	x						
Adverse event evaluation		x			x			x	x	x	x		x	
Correlatives: submission of tumor tissue ^e	x													
Correlatives: blood ^e	x							x					x	x (52 wks)

a. Pre-treatment evaluations will be performed within 4 weeks prior to registration, unless otherwise specified. This excludes imaging which will be eligible within 12 weeks of registration on study.

b. For women of childbearing potential, pregnancy test must be completed within 2 weeks of beginning treatment.

- c. CT neck and chest CT will be acceptable if done within 12 weeks of trial registration. PET/CT is optional and only recommended if there is concern for gross

- residual disease. MRI brain and/or orbits may be important for tumors near the skull base, especially those with perineural invasion. In these cases, MRI is recommended to be obtained at baseline, at wk 20 follow up, and at later follow up visits as clinically indicated. While the routine surveillance **images** are scheduled for weeks 20, 32 and 52, changes in patient symptoms or persistent symptoms may prompt the clinician to order a CT at any time, as per standard practice.
- d. Dental evaluation is recommended for those who will receive significant (>45Gy) dose of radiation to the mandible. However, it is not required.
 - e. Baseline tumor tissue will be sent to Merck for PD-1 testing. Blood will be collected at designated times (+/- 4 weeks to accommodate patient preference, transportation needs and scheduling needs around coordination of appointments) and sent to the [name] lab. Additional study of tumor tissue (fresh and/or FFPE) may be done if the patient has consented to other tissue banking protocols.

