7.1.2.5 Tumor Imaging and Assessment of Disease

As this is an adjuvant trial, there will be no anticipated measureable disease to record. RECIST and other such response criteria do not apply. However, there will be baseline imaging and surveillance imaging to evaluate for locoregional and distant recurrence as specified in the

Trial Flow Chart (section 6.0). In the event of clinical or radiographic recurrence of disease, biopsy to confirm recurrent disease is strongly recommended.

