8.3 Statistical Analysis Plan

DLT will be estimated using an exact 95% confidence interval. If 11 or more patients experience DLT the regimen will be considered too toxic. One-year PFS will be estimated using the Kaplan-Meier method and a 95% confidence interval constructed using Greenwood's method. One year PFS outcomes will be assessed overall and also separately for immunocompetent patients vs. immunosuppressed patients (e.g. CLL). These outcomes will be compared to our historical dataset for both subsets respectively. Adverse events will be tabulated by category and grade. The rates of

adverse events will be estimated using an exact 95% confidence. The relationship between 1yr PFS and baseline PD-L1 expression will be assessed using logistic regression. Immunoprofiles in peripheral blood in serial samples will be tested using random effects ANOVA. Bioinformatic analysis will be applied to all genomic and transcriptomic data.

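### Appendix 10.10 sends baseline PD-L1 results to the study investigators with no embargo, so knowing the marker could influence how recurrence is ascertained in the correlative analysis of 1-year PFS

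*Combined protocol and SAP*

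**What the plan says.** **Who receives the result.** Appendix 10.10, Study #1, states that "QualTek Molecular Laboratories Clinical Laboratories will report to Merck and study investigators". It gives no reporting date, does not say whether results come singly or in a batch, and sets no embargo. Specimens are "assigned a unique identification number. All other PHI will be redacted from the pathology report", which hides the patient from the laboratory but does not hide the result from the investigators. The same appendix has the research laboratory report the blood and tissue correlative results to Merck and the investigators as well.

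**When the specimen is taken.** It is a baseline specimen. The flow chart footnote in Section 6.1 reads "Baseline tumor tissue will be sent to Merck for PD-1 testing". I take this to be the same test that Section 4.2.3.3 and Appendix 10.10 call PD-L1. Section 4.2.3.3 sets the cut-off at 5% or more: "tumor cell membrane staining will be reported as positive".

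**How it is used.** Section 8.3: "The relationship between 1yr PFS and baseline PD-L1 expression will be assessed using logistic regression". The matching hypothesis in Section 3.2 is "Baseline PD-L1 expression will not be associated with 1yr PFS". Sections 5.1 to 5.4 and 7.1.5.3 make no use of PD-L1 for eligibility, treatment, allocation or follow-up.

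**How the outcome is ascertained.** Section 7.1.2.5 says that RECIST and similar criteria do not apply, and that "biopsy to confirm recurrent disease is strongly recommended". Routine imaging is at weeks 20, 32 and 52, but "changes in patient symptoms or persistent symptoms may prompt the clinician to order a CT at any time", in line with standard practice (Section 6.1, footnote c). Section 7.1.5.3 accepts visits up to 4 weeks before or after target. Section 8.1 defines PFS without naming who assesses progression.

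**The concern.** The trial is open label (Section 5.2.3), and the people following the patients may come to hold a marker result that they do not need for any protocol decision. The outcome later regressed on that marker depends partly on judgement: whether a symptom warrants a scan, whether an equivocal finding is called recurrence, and on what date. If those judgements differ by known PD-L1 status, the estimated association mixes biology with surveillance.

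A difference in surveillance could create an association where none exists or hide a real one. Because the stated hypothesis is no association, a reader would want to know that neither a positive nor a null result owes anything to assessors knowing the marker. At stake is the interpretation of correlative objective 1. The same applies to those blood and tissue analyses that Section 3.2 relates to 1-year PFS.

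**Working it through.** The plan gives no power, effect size, significance level or masking statement for the PD-L1 analysis, so there is no planned figure to reproduce. The check therefore has three parts.

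**1. Can ascertainment move an event across the 1-year mark?**
- Scheduled scans leave a gap of 52 − 32 = 20 weeks at nominal dates. Imaging detection within the gap depends on symptom-prompted CT.
- The week-52 visit may fall from week 52 − 4 = 48 to week 52 + 4 = 56. A recurrence first seen at week 50 is a 1-year event; the same recurrence first seen at week 55 is not. The logistic model needs a yes/no outcome at one year, so this timing matters.
- Deaths are PFS events, and their occurrence is not open to this influence.

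**2. What is one patient worth?** Input: 34 evaluable patients (Section 8.2). PD-L1 prevalence is not in the documents and is assumed.
- 30% positive: 0.30 × 34 = 10.2, taken as 10; 1/10 = 10 points of that group's 1-year PFS.
- 50% positive: 0.50 × 34 = 17; 1/17 = 5.9 points.

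This is the weight of one patient reclassified for any reason. It does not measure the bias.

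**3. What would a given amount of differential ascertainment do?** This is an illustration only. Assumptions: no true PD-L1 effect; 30%, 50% or 70% positive; 1-year PFS of 60%, 70% or 80%; and 10%, 20% or 30% of 1-year events in the PD-L1-negative group missed or dated after one year. The negative group is taken as the less closely watched one for illustration only.

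Formulas, with e = 1 − PFS, miss fraction m, and n₀ patients in the less watched group:
- events shifted = n₀ × e × m
- spurious odds ratio = [e/(1 − e)] ÷ [e(1 − m)/(1 − e(1 − m))]

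One case: 10 positive and 24 negative, PFS 70%, m = 20%.
- events shifted = 24 × 0.30 × 0.20 = 1.44
- odds ratio = (0.30/0.70) ÷ (0.24/0.76) = 0.429 ÷ 0.316 = 1.36

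Across the grid:

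| Quantity | Range |
|---|---|
| Events shifted | 0.2 to 2.9 |
| Spurious odds ratio | 1.14 to 1.71 |
| Exact Fisher rejection rate, nominal two-sided 5%, no shift | 1.9% to 2.9% |
| Same, with shift | 1.5% to 8.3% |

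Fisher's test on PD-L1 positive versus negative stands in for the logistic regression. Under these assumptions the estimate can be distorted noticeably, while a falsely significant result stays uncommon at this sample size.

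**The case against.** The strongest reply is that two links in the chain are not documented. Baseline describes the specimen, not the report, and a batch report after follow-up would remove the problem. No section names the assessor of recurrence. Both objections stand as limits: the documents show that the plan permits marker-aware assessment, not that it happens. The plan does not commit to late reporting, however, and describes no assessor other than the investigators.

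A reader might infer that investigators can order extra scans at will. The text does not support that. Footnote c of Section 6.1 ties an extra CT to changed or persistent symptoms and to standard practice, and every patient has the same routine schedule. What remains is that the clinician judges the symptoms.

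A reader might also infer that withholding PD-L1 would prevent ascertainment bias altogether. It would not. The visit windows, optional biopsy and absence of criteria would remain, and they affect 1-year PFS more directly.

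It is also fair to say that the direction of any bias is not established. Section 4.2.3.3 calls the marker's relation to response unknown, and Section 3.2 expects none, so the plan gives no reason to suppose that one group would be watched more closely. Nothing shows that unmasking would shift even one event. Finally, this is a correlative objective with no stated error rate or power.

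**Conclusion.** The point holds as a minor, inexpensive improvement. The plan routes a marker result to investigators with no embargo, has no use for it during follow-up, and then relates it to an outcome with room for judgement. Whether any bias would arise depends on two unstated facts: that results arrive during follow-up, and that investigators judge recurrence.

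The size and direction are unknown. The figures of 10 and 5.9 points are the weight of one patient under assumed prevalences, and should not be read as an estimate of bias. The odds ratios of 1.14 to 1.71 rest wholly on the assumed prevalence, PFS and miss fractions.

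A reader might infer that the primary results are compromised. The documents do not support that: neither the DLT rule nor the overall 1-year PFS estimate in Sections 8.2 and 8.3 uses PD-L1. The consequence is confined to the correlative analyses.

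**What to change.** Change the reporting line in Appendix 10.10, Study #1. PD-L1 results, under the unique identification number, go to Merck and to the study statistician or data management. They reach investigators only after the last patient's 1-year disease status is locked, and Merck does not forward them before then. Apply the same rule to the blood and tissue correlative results that Section 3.2 relates to 1-year PFS.

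Two details need adding. Name the recipient function, because the documents do not currently identify one. State in Section 10.6 that the investigator's access to marker results is deferred, not removed; the role-based access described there for OnCore could enforce this. If results are already reported in a batch after follow-up, a sentence saying so closes the point.

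The cost is a reporting instruction and later sight of the marker results by investigators. No care specified in the protocol depends on them. The change removes only the bias due to knowing the marker; the visit windows and optional biopsy are untouched.
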